## 4 INTRODUCTION

This PKAP has been developed after review of the Clinical Study Protocol CVL-354-1001 version 3.0, dated 25 May Sep2022 (1). This PKAP describes the planned analysis of the PK data from this study.

The intent of this document is to provide guidance for the PK and statistical analyses of PK data. In general, the analyses are based on information from the protocol, unless they have been modified by agreement between the Sponsor and Labcorp Drug Development (hereafter, referred to as Labcorp) Clinical Pharmacology Services. A limited amount of information concerning this study (eg, objectives, study design) is given to help the reader's interpretation. When the PKAP is agreed upon and finalized, it will serve as guidance for this study's PK report.

This PKAP supersedes the PK considerations identified in the protocol. If additional analyses are required to supplement the planned analyses described in this PKAP, they may be performed and identified in the PK report. Any substantial deviations from this PKAP will be agreed upon between the Sponsor and Labcorp Clinical Pharmacology Services and identified in the PK report.

### 4.1 Background

Kappa opioid receptor (KOR) activation is implicated in reduced activity of the reward (mesolimbic) pathway. Recent evidence suggests that selective antagonism of KORs may provide therapeutic benefit in treating major depressive disorder (MDD). CVL-354 is a brain-penetrant, potent KOR antagonist with >10-fold pharmacological selectivity over mu opioid receptors (MORs) that is being developed for treatment of MDD. Nonclinical data generated to date support development of CVL-354 for treatment of MDD.

The aim of this 2-part, first-in-human trial is to investigate the safety, tolerability, and pharmacokinetics (PK) of CVL-354, following single ascending dose (SAD) and multiple ascending dose (MAD) oral administration in healthy participants.

## 5 STUDY OBJECTIVES

The scope of this PKAP and the PK report will address a component of the following secondary objectives from the study protocol:

### Part A (Single Ascending Dose [SAD])

- To evaluate the plasma pharmacokinetics of CVL-354 following single ascending doses administered orally to healthy participants
  - Pharmacokinetics parameters of CVL-354 following single oral doses:
    - $C_{max}$
    - $T_{max}$
    - $AUC_{24}$
    - $AUC_{last}$
    - $AUC_{inf}$
    - $CL/F$
    - $V_z/F$

- $t_{1/2}$
- To evaluate the effect of food following single doses of CVL-354 administered orally to healthy participants
  - Pharmacokinetics parameters of CVL-354 following single oral doses:
    - $C_{max}$
    - $T_{max}$
    - $AUC_{24}$
    - $AUC_{last}$
    - $AUC_{inf}$
    - $CL/F$
    - $V_z/F$
    - $t_{1/2}$

## Part B (Multiple Ascending Dose [MAD])

[figure not shown]
- To evaluate the plasma pharmacokinetics of CVL-354 following multiple ascending doses administered orally to healthy participants
  - Pharmacokinetics parameters of CVL-354 on Days 1 and 14:
    - $C_{max}$
    - $T_{max}$
    - $C_{trough}$
    - $AUC_{\tau}$
    - $CL/F$  (Day 14 only)
    - $V_z/F$  (Day 14 only)
    - PTR (Peak-to-trough ratio) (Day 14 only)
    - $R_{ac}, C_{max}$  (Day 14 only)
    - $R_{ac}, AUC$  (Day 14 only)
    - $t_{1/2}$  (Day 14 only)
    - $A_e$  (Day 14 only)
    - $CL_R$  (renal clearance; Day 14 only)

## 6 STUDY DESIGN

This is a Phase 1, double-blind (investigator and participant), randomized, placebo-controlled, single-center trial that will be conducted in 2 parts to evaluate safety, tolerability, and PK of CVL-354 following single and multiple doses in healthy participants.

[figure not shown]
Information regarding the study design is detailed in the CVL-354-1001 Protocol version 3.0 (1).

### Figure 1: Study Design Schematics Part A (SAD, Cohorts 1 and 2)

[figure not shown]
Abbreviations: n=number of observations; R=randomization; Seq=sequence

### Part A (Food Effect, Cohort 3)

Abbreviations: IMP=investigational medicinal product; n=number of observations; R=randomization; Seq=sequence

## Part B (MAD, Cohorts 1-5)

Abbreviations: IMP=investigational medicinal product; N=number of participants; R=randomization.

## 6.1 SAD and Food Effect– Part A

### 6.1.1 SAD (Cohorts 1 and 2)

Dose escalation will proceed according to a double-blind (investigator and participant), 4-period crossover, single ascending dose methodology. Up to 2 cohorts of participants may be evaluated.

Cohorts 1 and 2 will be dosed in a sequential manner for up to 4 periods each. Progression to each dose level will occur following evaluation of all available cumulative safety, tolerability, PK, and other emergent data from the previous cohorts and periods. The current trial may evaluate up to 8 different dose levels in Cohorts 1 and 2; however, some doses may be repeated, if required. The starting dose for Part A will be 0.5 mg. Each dosing period will be separated by a washout period of at least 5 days.

Cohorts 1 and 2 will comprise of approximately 8 participants (3:1 ratio of CVL-354 to placebo within each treatment period). All participants will receive single oral doses of CVL-354 or placebo during each period.

Doses, in general, will be escalated in Cohort 1 and Cohort 2 until the maximum tolerated dose is achieved or the CVL-354 exposures ( $C_{max}$  and  $AUC_{24}$ ) reach, or are projected to reach, the predefined human exposure limits established based on the no observed adverse effect level (NOAEL) exposures [REDACTED]. Dose escalation may also be stopped if it is determined that sufficient exposures are achieved,

based on estimated target occupancy. Based on emergent data, the actual doses may change; however, new doses will not exceed half-log increments (3.3-fold) from previous dose. Smaller increments (eg,  $\leq$  2-fold) will be evaluated as exposures approach the proposed stopping criteria.

**Table 1: SAD Planned Dosing Levels**

Cohort a	N b	Period 1	Period 2	Period 3	Period 4
Cohort 1	2	Placebo	1.5 mg	5 mg	10 mg
	2	0.5 mg	Placebo	5 mg	10 mg
	2	0.5 mg	1.5 mg	Placebo	10 mg
	2	0.5 mg	1.5 mg	5 mg	Placebo
Cohort 2	2	Placebo	40 mg	80 mg	100 mg
	2	20 mg	Placebo	80 mg	100 mg
	2	20 mg	40 mg	Placebo	100 mg
	2	20 mg	40 mg	80 mg	Placebo

a Doses/treatments may be modified based on emergent safety, tolerability, and pharmacokinetic data or repeated to confirm safety/tolerability.

b N= Number of participants. Approximately 8 participants (3:1 ratio of CVL-354 to placebo within each treatment period). Sentinel dosing for each dosing period (n=2; 1 CVL-354 and 1 placebo) will be employed to ensure safety and tolerability before initiation of the rest of the cohort.

### 6.1.2 Food Effect Evaluation (Cohort 3)

Cohort 3 will be scheduled after completion of single dose escalation to evaluate the effect of food on CVL-354 exposures after a single 50 mg dose. The selected dose is 4-fold lower than the top single CVL-354 200 mg dose that is considered safe and tolerated. For evaluation of food effect, a 2-period crossover design will be utilized, with approximately 8 participants randomized to 1 of 2 sequences (fed/fasted or fasted/fed). The duration of each period will be 3 days, with a 2-day washout between Period 1 and Period 2.

### 6.2 MAD – Part B

The safety and PK of double-blind (investigator and participant), multiple-dose administration of CVL-354 will be evaluated in Part B of the trial after completion of dose escalation in Part A. Part B may overlap with Part A, Cohort 3 (evaluation of food effect on CVL-354 exposures).

Up to 5 sequential cohorts of 10 participants each will be evaluated in Part B. Participants will receive oral doses of either CVL-354 or placebo for up to 14 days. Eligible participants will be admitted to the clinic on Day -1 and will be randomized in a 4:1 ratio (8 participants active treatment: 2 participants placebo). Cohorts will be initiated in a sequential manner after review of all available safety, tolerability, and PK data (at least up to Day 15) from previous cohorts.

Each dose of CVL-354 will be administered once daily (QD) throughout Part B of the trial based on data obtained during Part A of the trial.

The starting dose for Part B will be 10 mg QD. In Part A, a single oral CVL-354 dose of 200 mg was deemed to be safe and well tolerated. The exposures from daily doses of 10 mg QD are expected to be well below the highest exposures investigated in the SAD part [REDACTED]

[REDACTED] During Part B, all preceding doses should be deemed safe and tolerated before progressing to higher

doses. Similar to Part A, dose increments in Part B will not exceed half-log increments (3.3-fold) early in escalation and smaller escalation steps ( $\leq 2$ -fold) will be implemented at doses closer to stopping criteria.

### 6.3 PK Stopping Criteria – Part A and Part B

- **SAD:** If, based on the observed data, the group mean  $C_{max}$  or  $AUC_{24}$  (based on total plasma concentrations) of the next planned dose is projected to exceed the exposure limits [REDACTED] that dose will not be explored. Modified doses may be explored if they are not expected to exceed PK stopping criteria.
- **MAD:** If, based on the observed data, the group mean steady state (Day 14)  $C_{max}$  or  $AUC_{24}$  (based on total plasma concentrations) of the next planned dose is projected to exceed the maximum exposure in SAD [REDACTED] [REDACTED], that dose will not be explored. Modified doses may be explored if they are not expected to exceed PK stopping criteria.

Progression to the next dose will occur if the last dose was tolerated and after satisfactory review of the available safety, tolerability, and PK data from a minimum of 6 participants (including at least 1 placebo participant) within a treatment period.

The dose increments will be based on observed exposures and forward predictions. The size of the exposure increments may be changed (not exceeding 3.3-fold [half-log] increments) as the trial progresses, dependent upon emerging PK, safety, and tolerability data. Any decision to change the size of the exposure increment will be made jointly by the investigator and the trial team and after careful evaluation of all available data.

### 6.4 Dose Administration

- All doses in Parts A, except for dosing under “fed” conditions, will be administered under fasted conditions following an overnight fast of at least 10 hours. Participants will continue to fast for 4 hours following dosing on Day 1.
- For dosing under “fed” conditions during food evaluation, following an overnight fast of at least 10 hours, participants will start breakfast approximately 25 minutes prior to administration of IMP. The IMP will then be administered within approximately 5 minutes of completion of the meal.
- For Part B, on days with intensive PK sampling (Day 1 and Day 14), the IMP will be administered under fasted conditions following an overnight fast of at least 10 hours. Participants will continue to fast for 4 hours following dosing on these intensive PK sampling days. On other days, each dose of IMP will be administered at approximately the same time each morning at least 1 hour following the morning meal.
- Each dose will be administered with 240 mL of water.

## 6.5 PK Sample Collections

Blood and urine (MAD part only) samples will be obtained during the study for measurement of CVL-354 concentrations in plasma and urine. For PK assessments, there will be an acceptable blood collection window of  $\pm 10\%$  of the nominal time point (eg, within 6 minutes of a 60-minute sample).

### **SAD and Food effect**

Serial PK blood samples (1 sample and 1 backup sample) will be collected during the SAD portion for each participant receiving drug and placebo at predose, 0.5, 1, 2, 3, 4, 6, 8, 12, 16, 24, 36, and 48 hours postdose. Predose PK samples (1 sample and 1 backup sample) will be obtained within 15 minutes prior to dosing.

### **MAD**

PK blood samples (1 sample and 1 backup sample) will be obtained predose (within 15 minutes prior to dosing) and 0.5, 1, 2, 3, 4, 6, 8, 12, 16, and 24 hours following administration of the first dose of IMP on Day 1 and on Day 14 at predose (within 15 minutes prior to dosing) and 0.5, 1, 2, 3, 4, 6, 8, 12, 16, 24, 36, 48, and 72 hours after the morning dose. A single predose PK sample will be taken on Days 3, 5, 7, 9, and 11.

Cumulative pharmacokinetic urine samples will be collected during the MAD study for each participant receiving drug and placebo on Day 14 (0-24 hour) postdose.

## 6.6 PK Sample Bioanalysis

Plasma and urine samples will be stored and shipped to Q2 Solutions who will perform bioanalysis of CVL-354 using a validated LC/MS/MS method to determine plasma and urine concentrations. The details of the bioanalysis method will be described in the bioanalysis plan prior to the analysis. Further instructions and details on the processing, collection, and handling of samples will be provided in separately defined Laboratory Manual.

## 7 ANALYSIS SETS

### 7.1 Safety Analysis Set

All randomized participants who receive at least 1 dose of IMP.

### 7.2 Pharmacokinetics Analysis Set

All participants in the Safety Analysis Set who have at least 1 quantifiable CVL-354 concentration.

## 8 PHARMACOKINETIC ANALYSIS

### 8.1 Pharmacokinetic Analysis

The following PK parameters will be determined where possible from the plasma and urine concentrations of CVL-354 using noncompartmental methods in validated software program Phoenix WinNonlin (Certara, Version 8.3.5 or higher):

## Part A\* (SAD and Food Effect)

Parameter	Units a	Definition
AUC last	h*ng/mL	area under the concentration-time curve from time zero to the time of the last quantifiable concentration b
AUC 24	h*ng/mL	area under the concentration-time curve over the time interval 0 to 24 hours postdose b
AUC inf	h*ng/mL	area under the concentration-time curve from time zero extrapolated to infinity b, c
%AUC extrap	%	percentage of area under the concentration-time curve due to extrapolation from the last quantifiable concentration to infinity
C max	ng/mL	maximum plasma concentration
T max	h	time to maximum plasma concentration
t last	h	time of the last quantifiable concentration
t 1/2	h	apparent terminal elimination half-life
CL/F	L/h	apparent clearance of drug from plasma
V z/F	L	apparent volume of distribution during the terminal phase
DAUC last	h*ng/mL/mg	AUC last normalized by dose administered d
DAUC 24	h*ng/mL/mg	AUC τ normalized by dose administered d
DAUC inf	h*ng/mL/mg	AUC inf normalized by dose administered d
DC max	ng/mL/mg	C max normalized by dose administered d

a Units are based on concentration units (provided by the bioanalytical lab or preferred units for presentation of PK parameters) and dose units used in the study.

b The area under the concentration-time curve will be calculated using the linear trapezoidal rule for increasing concentrations and the logarithmic rule for decreasing concentrations (linear up/log down rule).

c Based on the last observed quantifiable concentration.

d Calculated by dividing the parameter by the dose (mg).

\* Concentration-time profile following each discrete single dose in Part A Profile Day 1, including all periods of the food effect evaluation.

## Part B\*

Parameter	Units a	Definition
AUC last	h*ng/mL	area under the concentration-time curve from time zero to the time of the last quantifiable concentration b
AUC 24	h*ng/mL	area under the concentration-time curve over the time interval 0 to 24 hours postdose (Day 1 only) b
AUC inf	h*ng/mL	area under the concentration-time curve from time zero extrapolated to infinity (Day 1 only) b, c

%AUC extrap	%	percentage of area under the concentration-time curve due to extrapolation from the last quantifiable concentration to infinity (Day 1 only)
AUC τ	h*ng/mL	area under the concentration-time curve over a dosing interval ( $\tau$ ) (Day 14 only) b,d
C max	ng/mL	maximum plasma concentration
C trough	ng/mL	trough plasma concentration; observed at the end of the dosing interval
%Fluctuation	%	percentage fluctuation at steady state, equivalent to peak-to-trough ratio (PTR) in the protocol
T max	h	time to maximum plasma concentration
t last	h	time of the last quantifiable concentration
t 1/2	h	apparent terminal elimination half-life (Day 14 only)
CL/F	L/h	apparent clearance of drug from plasma (Day 14 only)
V z /F	L	apparent volume of distribution during the terminal phase (Day 14 only)
Rac, AUC τ	NA	accumulation ratio based on AUC τ (Day 14 only)
Rac, C max	NA	accumulation ratio based on C max during the dosing interval (Day 14 only)
LR	NA	linearity ratio (Day 14 only)
Ae t1-t2	mg	amount of the dose administered recovered in urine over a dosing interval (t 1 to t 2 ) at steady state (Day 14 only)
Cum Ae t1-t2	mg	cumulative amount of the dose administered recovered in urine over a dosing interval (t 1 to t 2 ) at steady state (Day 14 only)
fe t1-t2	%	percentage of the dose administered recovered in urine over a dosing interval (t 1 to t 2 ) at steady state (Day 14 only)
Cum fe t1-t2	%	cumulative percentage of the dose administered recovered in urine over a dosing interval (t 1 to t 2 ) at steady state (Day 14 only)
CL R	L/h	renal clearance of drug from plasma (Day 14 only)
DAUC τ	h*ng/mL/mg	AUC τ normalized by dose administered c
DAUC last	h*ng/mL/mg	AUC last normalized by dose administered c
DC max	ng/mL/mg	C max normalized by dose administered c

a Units are based on concentration units (provided by the bioanalytical lab or preferred units for presentation of PK parameters) and dose units used in the study.

b Area under the concentration-time curve will be calculated using the linear trapezoidal rule for increasing concentrations and the logarithmic rule for decreasing concentrations (linear up/log down rule).

c Calculated by dividing the parameter by the dose administered (mg).

d The dosing interval  $\tau$  throughout part B will be 24 hours.

e Based on the last observed quantifiable concentration.

\* Concentration-time profile following multiple dosing on Profile Day 1 and Day 14.

NA = not applicable

Additional PK parameters may be determined where appropriate.

Pharmacokinetic analysis will be carried out where possible using actual dose administered (mg) and actual postdose blood sampling times. If an actual time is missing, the sample concentration result will be treated as missing unless there is scientific justification to include the result using the nominal time.

The parameters  $C_{max}$ ,  $C_{trough}$ ,  $t_{last}$ , and  $T_{max}$  will be obtained directly from the concentration-time profiles. If  $C_{max}$  occurs at more than 1 timepoint,  $T_{max}$  will be assigned to the first occurrence of  $C_{max}$ .

Predose (trough) plasma concentrations on dosing days 3, 5, 7, 9 and 11 will be listed.

The accumulation ratio(s) ( $R_{ac}$ , AUC and  $R_{ac}$ ,  $C_{max}$ ) will be calculated as follows:

$$R_{ac}, \text{AUC} = \text{AUC}_\tau \text{ Profile Day 14} / \text{AUC}_{24} \text{ Profile Day 1}$$

$$R_{ac}, C_{max} = C_{max} \text{ Profile Day 14} / C_{max} \text{ Profile Day 1}$$

The linearity ratio (LR) will be calculated as ratio of  $\text{AUC}_\tau$  following multiple dosing (Day 14) to  $\text{AUC}_{inf}$  following a single dose (Day 1):

$$LR = \text{AUC}_\tau \text{ Profile Day 14} / \text{AUC}_{inf} \text{ Profile Day 1}$$

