To evaluate the plasma pharmacokinetics of CVL-354 following multiple ascending doses administered orally to healthy participants	 Pharmacokinetic parameters for CVL-354 on Days 1 and 14: C_{max} T_{max} C_{trough} AUCτ CL/F (Day 14 only) V_Z/F (Day 14 only) PTR (Day 14 only) Rac, C_{max} (Day 14 only) Rac, AUC (Day 14 only) t_{1/2} (Day 14 only) Ae (amount eliminated unchanged in urine at steady state on Day 14) Renal clearance 	

Abbreviations: AE=adverse event; AUC=area under the concentration-time curve; CL/F=apparent clearance of drug from plasma; C_{max} =maximum plasma concentration; C_{trough} =trough plasma concentration; C-SSRS=Columbia-Suicide Severity Rating Scale; ECG=electrocardiogram; MAD=multiple ascending dose; PTR=peak-to-trough ratio; Rac=accumulation ratio; $t_{1/2}$ =apparent terminal half-life; T_{max} =time to maximum plasma concentration; V_z /F=apparent volume of distribution during terminal phase.

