### 3 ABBREVIATIONS

%AUC extrap	percentage of area under the concentration-time curve due to extrapolation from the last quantifiable concentration to infinity
%Fluctuation	percentage fluctuation at steady state
A e	amount of the dose administered recovered
A et1-t2	amount of the dose administered recovered in urine over the time interval t 1 to t 2 at steady state
ANOVA	analysis of variance
AUC	area under the concentration-time curve
AUC 24	area under the concentration-time curve over the time interval 0 to 24 hours postdose
AUC inf	area under the concentration-time curve from time zero extrapolated to infinity
AUC last	area under the concentration-time curve from time zero to the time of the last quantifiable concentration
AUC τ	area under the concentration-time curve over a dosing interval ( $\tau$ )
BID	twice daily
BLQ	below the limit of quantification
C avg	average plasma concentration
CI	confidence interval
CL/F	apparent clearance of drug from plasma
CL R	renal clearance
C max	maximum plasma concentration
CSR	clinical study report
C trough	trough plasma concentration
CV	coefficient of variation
DAUC 24	area under the concentration-time curve over a dosing interval ( $\tau$ ) normalized by dose administered
DAUC inf	area under the concentration-time curve from time zero extrapolated to infinity normalized by dose administered
DAUC last	area under the concentration-time curve from time zero to the time of the last quantifiable concentration normalized by dose administered
DAUC τ	area under the concentration-time curve over a dosing interval ( $\tau$ ) normalized by dose administered
DC max	maximum plasma concentration normalized by dose administered
fe	percentage of the dose administered recovered
fe t1-t2	percentage of the dose administered recovered in urine over the time interval t 1 to t 2 at steady state
GLSM	geometric least squares mean
IMP	investigational medicinal product

KOR	Kappa opioid receptor
$\lambda_z$	apparent terminal elimination rate constant
$\lambda_z$ Lower	start of exponential fit
$\lambda_z$ N	number of data points included in the log-linear regression

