$\lambda_z$ Span Ratio	time period over which apparent terminal elimination rate constant was determined as a ratio of apparent terminal half-life
$\lambda_z$ Upper	end of exponential fit
LC/MS/MS	liquid chromatography with tandem mass spectrometry
ln	natural log
LR	linearity ratio
LSM	least squares mean
MAD	multiple ascending dose
max	maximum
MDD	major depressive disorder
min	minimum
MOR	mu opioid receptors
N	number of participants
n	number of observations
NA	not applicable
NC	not calculated
NOAEL	no observed adverse effect level
PK	pharmacokinetic(s)
PKAP	pharmacokinetic analysis plan
PTR	peak to trough ratio
QD	once daily
R	randomization
Rac	accumulation ratio
Rac, AUC τ	accumulation ratio based on area under the concentration-time curve over a dosing interval ( $\tau$ )
Rac, C max	accumulation ratio based on maximum plasma concentration during the dosing interval
SAD	single ascending dose
Seq	sequence
SD	standard deviation
SOP	Standard Operating Procedures
SRT	Safety Review Team
TBD	to be determined
t last	time of the last quantifiable concentration

$T_{max}$  time to maximum plasma concentration  
 $t_{1/2}$  apparent terminal elimination half-life  
 $V_z/F$  apparent volume of distribution during the terminal phase

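### The PK analysis plan gives the Day 14 peak-to-trough ratio, a secondary endpoint, no row or formula, and wrongly treats percentage fluctuation as equivalent to it

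*SAP*

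**What the plan says.** The protocol lists PTR, restricted to Day 14, among the secondary PK endpoints of Part B, both in the synopsis and in Section 3, Table 7. It expands the abbreviation as "PTR=peak-to-trough ratio". SAP Section 2, Table 2 and PKAP Section 5 repeat the endpoint with the same Day 14 restriction.

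PKAP Section 8.1 sets out which parameters will be computed. Its Part B table has no PTR row. The only mention of PTR is in the %Fluctuation row, whose unit is % and whose definition reads "percentage fluctuation at steady state, equivalent to peak-to-trough ratio (PTR) in the protocol". The text below the table writes out formulas for the accumulation ratios and the linearity ratio. No formula for %Fluctuation or for PTR appears in the protocol, the SAP or the PKAP.

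The PKAP abbreviation list (Section 3) has separate entries for the two terms: "percentage fluctuation at steady state" for %Fluctuation and "peak to trough ratio" for PTR.

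Two other statements decide what follows from this. PKAP Section 4 gives the PKAP precedence over the protocol on PK matters. PKAP Section 9.1 limits summary statistics to data that the PKAP details.

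**The concern.** A ratio of two concentrations and a percentage difference between them are different quantities on different scales. Calling them equivalent puts another metric in the place of a pre-specified secondary endpoint while stating that nothing has changed. Because the denominator of %Fluctuation is not stated, a reader of the report could not tell how to convert the result back to PTR, or whether conversion is possible at all.

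The PKAP also disagrees with itself: Section 5 promises PTR and Section 8.1 does not plan it. Since the PKAP overrides the protocol, Section 8.1 is what a programmer would follow. The report must record departures from the PKAP (Section 10.2). Reporting %Fluctuation would follow the PKAP, so that requirement would not bring the substitution to light.

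**Working it through.** The plan states no figure to reproduce, so the check is of the definitions, followed by an illustration of size.

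**Definitions.** All three are assumptions, because the documents give no formula. The trough is the concentration at the end of the 24 h dosing interval, as the PKAP defines Ctrough.

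- PTR = Cmax / Ctrough (the natural reading of the name)
- F1 = 100 × (Cmax − Ctrough) / Cavg (fluctuation relative to the average)
- F2 = 100 × (Cmax − Ctrough) / Ctrough (fluctuation relative to the trough)

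**Algebra.** F2 = 100 × (PTR − 1), so F2 can be converted to PTR but is not PTR. F1 = 100 × (PTR − 1) × (Ctrough / Cavg), so F1 cannot be converted without Cavg. The PKAP abbreviates Cavg but does not list it as a Part B parameter.

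**Numerical example** (arbitrary concentrations). Cmax 100 and Ctrough 20 give PTR = 100/20 = 5.0 and F2 = 100 × 80/20 = 400%. F1 depends on Cavg:

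- Cavg 30: 100 × 80/30 = 267%
- Cavg 40: 100 × 80/40 = 200%
- Cavg 60: 100 × 80/60 = 133%

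Conversely, F1 = 200% also results from Cmax 85, Ctrough 5 and Cavg 40 (100 × 80/40), where PTR = 85/5 = 17.

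**Model illustration.** The visible text gives no absorption rate or half-life for CVL-354, so both are assumed. The model is one-compartment oral dosing at steady state with τ = 24 h:

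C(t) ∝ [ka/(ka − k)] × [e^(−kt)/(1 − e^(−kτ)) − e^(−ka·t)/(1 − e^(−ka·τ))], with k = ln 2 / half-life.

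At ka = 1/h:

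| Half-life (h) | PTR | F1 | F2 |
|---|---|---|---|
| 6 | 10.77 | 204% | 977% |
| 8 | 5.87 | 158% | 487% |
| 12 | 3.22 | 109% | 222% |
| 18 | 2.17 | 74% | 117% |
| 24 | 1.78 | 56% | 78% |

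As a check on the 12 h row, Ctrough/Cavg is 0.490, so F1 = 100 × (3.221 − 1) × 0.490 = 109%.

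Over ka 0.5 to 2/h and half-life 6 to 24 h, PTR runs from 1.65 to 12.7, F1 from 48% to 230% and F2 from 65% to 1171%.

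**How loose the F1 mapping is in this model.** For ka of 0.3, 0.5, 1, 2 and 4/h, with the half-life solved so that PTR = 3.0, F1 is 95.8%, 98.9%, 102.8%, 105.5% and 107.2%; F2 is 200% each time. With the half-life solved so that F1 = 109%, PTR is 3.60, 3.41, 3.22, 3.12 and 3.06.

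**Day restriction.** The table footnote covers both profile days ("Concentration-time profile following multiple dosing on Profile Day 1 and Day 14"). The %Fluctuation row carries no Day 14 tag, whereas the urinary rows in the same table carry both the steady-state wording and the tag.

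**The case against.** The best defence is that this is an open substitution. PTR is named in the row, so the reader is told which protocol endpoint the row serves, and PKAP Section 4 allows PK analyses to be modified by agreement between the sponsor and the PK vendor. It is fair to say that PTR has been mapped to the wrong quantity, not forgotten. But stating a false equivalence does not disclose a change of metric, and Section 5 of the same plan still lists PTR.

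Several narrower points stand in whole or in part:

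- The steady-state wording in the row already implies Day 14, so the missing tag is minor.
- Two abbreviation entries alone prove little. They only show that the PKAP uses both terms.
- Other parameters, such as CL/F, are also defined without formulas. The gap matters here because the denominator of %Fluctuation is ambiguous.
- PTR = Cmax/Ctrough is itself a reading of the name. The documents do not rule out the interval minimum as denominator. In the model above the two coincide; in real profiles they need not.
- The F1 mapping is fairly tight in a one-compartment model (96% to 107% at PTR 3.0), and the % unit makes it unlikely that a reader would take 222% for a ratio.
- With the trough denominator, the mean, median, minimum and maximum of PTR follow exactly from those of F2 as 1 + F2/100. The geometric mean and geometric CV, which PKAP Section 9.1 also requires, do not.

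It is also true that additional parameters may be computed under Section 8.1, and that the table shells, a separate document not available here, may already carry PTR. The first is discretionary and does not name PTR. The second would leave Sections 5 and 8.1 in conflict.

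**Conclusion.** The concern holds. As written, PKAP Section 8.1 replaces a named secondary endpoint with a different quantity whose formula is not stated, and the claimed equivalence is false under both candidate definitions. In the illustration, a PTR of 3.2 would be reported as 109% or 222%. These figures rest on an assumed model, ka and half-life and say nothing about CVL-354 itself. The algebraic result does not depend on the model; it needs only that PTR means peak divided by trough.

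The consequence is limited. The endpoint is descriptive and no hypothesis is tested. The PK stopping criteria (Protocol Section 4.4, PKAP Section 6.3) use Cmax and AUC24 only, and no data are lost, because each participant's PTR follows from Day 14 Cmax and Ctrough. What would be missing is the by-dose summary: the median, range and CV of PTR cannot be read from separate summaries of Cmax and Ctrough. This should be corrected, but it does not threaten the trial's conclusions.

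**What to change.** In the PKAP Section 8.1 Part B table:

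1. Add a row for PTR: unitless, Cmax / Ctrough, Day 14 only.
2. Delete the statement that %Fluctuation is equivalent to PTR.
3. If %Fluctuation is kept, list it as a separate additional parameter with its formula, including the denominator, and restrict it to Day 14.
4. Add PTR to Table 14.2.1.2b and Listing 16.2.6.1.4 if the shells do not already carry it.

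Make the change before database lock. The cost is a wording change and one derived variable from two parameters already planned. Sampling and trial conduct are unaffected.
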